4.3. Phase 3 Semi-Structured Interview

We will follow a semi-structured interview guide to conduct telephone interviews with participants who completed at least the How to Use tutorial of the ITW (see "Phase 3 Interview Guide"). In the interviews, participants will be asked to provide feedback on their use of the ITW and will also provide input on potential future adaptations or applications of the ITW. Each interview will last up to 45 minutes.

4.4. Risk of Harm

This study involves research that presents very little risk. There are no physical risks or side effects associated with the study. Potential emotional risks of study participation include possible discomfort or distress associated with answering questions about melanoma, including the potential for disease recurrence. Based on our prior experience conducting research with cancer patients, the likelihood that participants in this study will experience such discomfort or distress is low.

It is possible that a participant may feel upset or distress if, while conducting a SSE, he/she identifies a suspicious lesion. During the course of the study, patients will remain under the clinical care of their physician at Rutgers CINJ, the Department of Dermatology at Rutgers RWJMS,Saint Barnabas Medical Center, and their respective physician from the NJSCR. As part of the informed consent process, patients will be encouraged to seek medical care with their physician if at any time they identify a suspicious lesion.

As with all research that collects protected health information, there is a risk that participants' confidentiality could be compromised during the study.

4.5. Protections Against Risks

Participants will be encouraged to contact the research team if they experience emotional discomfort or distress at any time during the study. All research staff will receive training to appropriately identify and handle instances when a patient would benefit from a referral (e.g., to a clinical social worker at Rutgers CINJ or Rutgers RWJMS) for follow-up of emotional discomfort or distress. If at any time during the study, a patient indicates concern about a suspicious lesion to a member of the research team, he/she will be advised to contact his/her treating physician to receive appropriate medical care.

In order to preserve privacy and protect the confidentiality of participants, a series of security procedures will be undertaken. IRB and HIPAA regulations concerning confidentiality will be strictly enforced. All study personnel receive training and certification in human subjects protection and HIPAA regulations. Each study participant will be given a unique numeric identifier upon study entry. Names and other protected health information will not be stored in the same database as survey and medical information. All computers used for research purposes adhere to the institution's requirements regarding password protection, data encryption, anti-virus protection, and intrusion detection. All Internet-based data communications will be encrypted. This includes transfer of electronic data between Rutgers University and the University of Virginia. All hard copy study-related materials and data will be stored in locked file cabinets in secure locations. The research teams at Rutgers University and the University of Virginia have never previously experienced a breach of participant confidentiality in a research study.

Protocol Version Date: 4/5/22

4.6. Potential for Benefit

This research has potential benefits for the study participants as well as for future patients diagnosed with melanoma. Participants who are eligible to take part in the study have a personal history of melanoma and do not currently engage in thorough SSE or sun protection behaviors. This study utilizes an Internet-based approach to promote patients' engagement in thorough SSE and sun protection behaviors. Thus, it is possible that for some study participants, a recurrence of their melanoma or new primary melanoma (or non-melanoma skin cancer) might be identified at an earlier time than would otherwise have been the case. If the intervention is found to promote skin surveillance and sun protection behaviors among melanoma patients, it has the potential to be utilized with broader populations of melanoma patients. Currently, more than 920,000 individuals in the U.S. are living with a personal history of melanoma. There is a critical need to develop effective interventions to promote thorough SSE and sun protection behaviors among melanoma patients. The current research addresses this important issue. By developing and testing an Internet-based intervention, this project has the potential to identify an efficacious, cost-effective, and disseminable approach for promoting skin surveillance and sun protection behaviors among melanoma patients across the country.

5. Data Handling and Statistical Analysis

5.1. Primary Aim

Aim 1. To evaluate the impact of the ITW versus Usual Care on SSE and sun protection behaviors among individuals diagnosed with melanoma. Hypothesis. Individuals assigned to the ITW will be more likely to engage in SSE and sun protection behaviors than those assigned to Usual Care.

Using intent-to-treat analyses, we will compare engagement in thorough SSE and the sun protection behavior index for individuals in the ITW versus Usual Care, with the outcomes at 24 weeks as the primary focus. To handle missing data due to participant dropout, weighted generalized estimating equations (Little & Rubin, 2002; Preisser et al., 2002; Robins et al., 1995), with a logit link for SSE (a binary variable) and an identity link for the sun protection behavior index, will be used to estimate the treatment effect with weights proportional to the inverse of the estimated probability of dropout. Score tests and estimates of regression coefficients for the treatment indicator variable will assess the effect of the intervention. Sensitivity analyses will examine the effect of intervention at follow-up controlling for any demographic information that differs significantly by intervention group at baseline. These analyses are appropriate under the assumption that dropout is missing at random (MAR). Secondary analyses will use multiple imputation to examine the estimated treatment effect under different scenarios assuming the dropout is missing not at random (MNAR). In particular, for the sun protection behavior index, the mean for treated dropouts will be assumed equal to the estimated mean for Usual Care non-dropouts plus a sensitivity parameter, set at values of 25%, 50%, 75% and 100% of the estimated treatment effect (representing scenarios ranging from dropouts experiencing almost all to none of the estimated treatment effect). These analyses provide a picture of potential bias due to informative dropout (Little, 1994; Minini & Chavance, 2004a, 2004b; National Research Council, 2010). Additional multilevel models (Raudenbush, 2003) will examine the effect of the intervention on changes in thorough SSE and sun protection behaviors over time, comparing changes across 8, 24 and 48 weeks. Specifically, generalized estimating equations will be used for estimation and testing (Liang & Zeger, 1986; Ukoumunne & Thompson, 2001). Additional analyses will focus on the effect of the intervention on the number of SSEs performed, the number of body areas examined, and the individual sun protection behaviors (wearing sunscreen with an SPF \geq 30, wearing a long-sleeved shirt, wearing a wide-brimmed hat, and staying in the shade). Analyses will also focus on the effect of the intervention on use of sunglasses, wearing long pants, spending time in the sun in order to get a tan, and the number of sunburns.

Protocol Version Date: 4/5/22

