3.6. Sample Size

Up to 30 individuals will take part in Phase 1 of the project. For Phase 2 of the project, we will recruit 420 participants. For Phase 3 of the project, we will recruit up to 50 participants. For the Phase 2 RCT study,

we conducted power calculations for the primary and secondary aims. (We did not conduct power calculations for Aim 3 because it is an exploratory aim.) For the primary aim (intervention efficacy), there are two primary outcomes: engagement in thorough SSE (binary outcome) and sun protection behavior index (continuous score) at 24 weeks post-baseline. At baseline, we anticipate that 9% of participants will be adherent to thorough SSE. Based on our own and others' prior research (Glanz et al., 2010; Janda et al., 2011; Manne et al., 2010; Weinstock et al., 2007), we anticipate that the rate of adherence to thorough SSE at 24 weeks post-baseline will be ≥35% in the ITW group and this will be at least 15 percentage points higher than the adherence rate in the Usual Care group. An increase in SSE of this magnitude would be considered a successful rate. We assume proportions of individuals completing SSEs are compared between treatments using a z-test. Allowing for 10% dropout at 24 weeks (a rate comparable to that experienced in our prior research; Manne et al., 2010) and an adherence rate to thorough SSE of up to 20% in the Usual Care group at 24 weeks post-baseline (which is at the upper end of what might be expected), 153 individuals would need to be recruited in each group to obtain 80% power. Power calculations for the sun protection behaviors outcome are based on results of prior tailored interventions, including our own (Glanz et al., 2010; Manne et al., 2010). In our prior RCT, sun protection scores at baseline were 2.8 for both groups and increased to 3.2 and 3.4 for the generic and tailored interventions, respectively. Given that the Usual Care control group in the current RCT is not an active control (the generic intervention in the prior study was an active control), we assume that the sun protection scores in that group would increase to a maximum of 3.0. Standard deviations were, on average, 0.66 at baseline and 0.76 at follow-up. We assume a correlation between baseline and follow-up measures of 0.60. Under these assumptions, recruiting 153 individuals to each group would provide more than 80% power to detect differences in changes in sun protection scores from baseline to 24 weeks post-baseline. For the secondary aim (intervention mediators), we utilized sample size tables for mediated effects based on simulation studies that model the two pieces of the mediating path (from intervention group assignment to mediating variable and from mediating variable to outcome) (Fritz & Mackinnon, 2007). Based on the results of relevant prior research, we conservatively assume that one of the two paths will have a regression coefficient of at least .14 (a small effect, according to Cohen's [1998] criteria) and the other will have a regression coefficient of at least .26 (a small-to-moderate effect). Under those assumptions, and allowing for 10% dropout at 24 weeks, recruiting 210 individuals to each group would provide 80% power to detect mediational effects (Fritz & Mackinnon, 2007). Overall, based on a consideration of the aforementioned factors, we will recruit 210 individuals to each of the ITW and Usual Care groups, for a total sample size of N = 420, which will provide at least 80% power for the primary and secondary aims. We anticipate that at least 378 of the 420 patients (i.e., 90%) will complete the 24 weeks post-baseline assessment and 357 (85%) will complete the 48 weeks post-baseline assessment.

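### The primary sun-index model in section 5.1 does not say how the baseline index enters; naming a 24-week contrast adjusted for baseline and strata costs nothing and may gain precision

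*Combined protocol and SAP*

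**What the plan says.** Section 5.1 compares the arms on the sun protection behavior index "with the outcomes at 24 weeks as the primary focus", using weighted GEE with an identity link to handle dropout. The test is described in one sentence: "Score tests and estimates of regression coefficients for the treatment indicator variable will assess the effect of the intervention". That model lists no covariates. Two related analyses appear nearby. One is a sensitivity analysis that controls for demographics found to differ significantly between arms at baseline. The other is a set of additional models of change over time, "comparing changes across 8, 24 and 48 weeks".

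Section 3.6 sizes the same outcome differently. It claims more than 80% "power to detect differences in changes in sun protection scores from baseline to 24 weeks post-baseline" with 153 recruited per group. Its inputs are: "Standard deviations were, on average, 0.66 at baseline and 0.76 at follow-up"; and "We assume a correlation between baseline and follow-up measures of 0.60".

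Section 3.2 has the baseline survey completed before randomisation, which is stratified by disease stage and time since diagnosis. Table 1 lists sun protection behaviors at baseline and at every follow-up.

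**The concern.** The sample size section works with change from baseline. The primary analysis section tests a treatment coefficient and does not mention baseline. At least three estimators fit the text: the difference in 24-week scores, the difference in change, and the 24-week difference adjusted for the baseline index. Under randomisation with an identity link all three estimate the same mean difference, so the choice does not alter the question being answered. It does alter the standard error, and a reader cannot tell in advance which estimate will be reported as the primary sun-index result. A baseline measure with an assumed correlation of 0.60 is collected from everyone before allocation, and the primary model does not clearly use it.

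**Working it through.** **Inputs.** From section 3.6: SD 0.66 at baseline and 0.76 at follow-up; correlation r = 0.60; baseline mean 2.8; Usual Care rising to at most 3.0; and, from the prior trial, scores that "increased to 3.2 and 3.4 for the generic and tailored interventions, respectively". Taking 3.4 for the ITW arm is a reading, since the text does not state that value outright. It gives a planned difference of 3.4 − 3.0 = 0.4. For completers, "We anticipate that at least 378 of the 420 patients (i.e., 90%) will complete the 24 weeks post-baseline assessment", so 378/2 = 189 per arm, assuming equal dropout. Alpha is not stated; two-sided 0.05 is assumed.

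**The plan's own figure.** The SD of change is √(0.66² + 0.76² − 2 × 0.60 × 0.66 × 0.76) = √0.4113 = 0.6413. With 153 recruited and 10% dropout, about 137 per arm remain, so SE = 0.6413 × √(2/137) = 0.0775. Power = Φ(0.4/0.0775 − 1.96) = 99.9%. The claim of more than 80% is met. Follow-up scores alone would also meet it at 137 per arm (99.2%).

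**Three estimators at 189 per arm.** SE = SD × √(2/189); half-width = 1.96 × SE.

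| Estimator | SD | Variance | SE | 95% CI half-width |
|---|---|---|---|---|
| 24-week score only | 0.76 | 0.5776 | 0.0782 | 0.153 |
| Change from baseline | 0.6413 | 0.4113 | 0.0660 | 0.129 |
| Adjusted for baseline | 0.76 × √(1 − 0.60²) = 0.608 | 0.3697 | 0.0625 | 0.123 |

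Variance ratios: 0.3697/0.5776 = 0.64, a 36% saving against follow-up only; 0.3697/0.4113 = 0.90, a saving of about 10% against change. To match the adjusted analysis, follow-up only would need 189/0.640 = 295 completers per arm and change 189/0.899 = 210.

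**Power at 0.4.** Φ(0.4/SE − 1.96) gives 99.9% for follow-up only and above 99.9% for the other two.

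**Dependence on r.** The variance saving from adjustment, over an assumed range of r:

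| r | Against follow-up only | Against change |
|---|---|---|
| 0.40 | 16% | 21% |
| 0.50 | 25% | 15% |
| 0.60 | 36% | 10% |
| 0.70 | 49% | 5% |

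Below r = 0.66/(2 × 0.76) = 0.43, change is less precise than follow-up only. The adjusted contrast is at least as precise as both at every r.

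**Dropout weights.** The table weights completers equally. Simulation checked the effect of weighting: 210 per arm, normal scores with the plan's SDs and r, and 10% dropout related to the baseline index at an assumed log odds ratio of 0 to 1.0 per SD. With conventional weights (inverse probability of being observed), the SEs were 0.078–0.079, 0.066–0.067 and 0.062–0.063, and the variance ratios 0.64–0.65 and 0.88–0.90. Section 5.1 literally describes weights inverse to the probability of dropping out. Taken at its word, and at the strongest dropout relation (log odds ratio 1.0), the SEs rise to about 0.15, 0.11 and 0.10, with ratios of roughly 0.41 and 0.79. The ratios vary between runs because such weights are very unequal. Adjustment then helps at least as much, but the SEs in the table no longer describe the analysis.

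**The case against.** The strongest reply is that nothing in section 5.1 excludes baseline from the model. If the sponsor already meant it as a covariate, the gain is zero. If section 3.6 is read together with section 5.1, change from baseline is at least as natural a reading as follow-up only, and the half-width then moves only from 0.129 to 0.123 on a 5-point scale. Section 5.3 does not settle the matter: it speaks of change from baseline, but in models said to resemble those of Aim 1. All of this stands. The saving lies between 0% and 36% depending on intent, and what is established is a missing specification.

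Three stronger inferences are tempting and are not supported.

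- **That the sun-index analysis is underpowered or invalid.** A follow-up-only comparison is valid under randomisation, and power at 0.4 exceeds 99% whichever estimator is used, with equal or conventional weights. A difference of 0.2 would give 73%, 86% and 89% for the three estimators. But 0.2 was the gap between the tailored intervention and an active control, and section 3.6 sets that comparison aside because Usual Care is not active. It is an illustration only.
- **That the single treatment coefficient averages over visits.** Section 5.1 does not say which visits enter the weighted GEE, but sections 3.6 and 5.1 both put the primary outcome at 24 weeks, which largely answers this. A clarifying phrase is enough.
- **That the rule for picking demographics in the sensitivity analysis undermines the result.** Selecting on baseline significance picks out chance imbalances rather than prognostic factors, but it cannot change the primary estimate.

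**Conclusion.** The point holds as a free improvement, for the sun protection index only. The primary model does not say how the baseline index enters, while the sample size section relies on it. A 24-week contrast adjusted for baseline has an SE of 0.0625, against 0.0782 for follow-up only and 0.0660 for change: 36% and about 10% less variance respectively, and no gain if baseline was already intended as a covariate. These figures rest on the plan's SDs and r = 0.60, 189 completers per arm, and equal or conventional weights. No precision gain is claimed for the strata, because the documents give no figure for it; they belong in the model because randomisation used them. The benefit is a narrower interval and an estimator fixed in advance. Neither validity nor planned power depends on it.

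**What to change.** In section 5.1, state that the primary sun-index contrast is ITW versus Usual Care at 24 weeks, whether from 24-week data alone or from a treatment-by-visit term if all visits are modelled. State that it is adjusted for the baseline sun index, disease stage (in the categories used for randomisation, which section 3.2 should give) and the time-since-diagnosis stratum. Have section 3.6 refer to that model.

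Optionally, replace the sensitivity analysis that selects demographics by baseline significance with covariates named in advance.

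The cost is wording only. The baseline index is already collected before randomisation and the strata are known at allocation, so no data, visits or participants are added. With an identity link, adjustment leaves the mean difference being estimated unchanged. That does not carry over to the logit model for SSE, where adjustment changes the odds ratio being estimated, so no change is asked for there.

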5.2. Secondary Aim

Aim 2. To examine mediators of the impact of the intervention. Hypothesis. The effects of the intervention on SSE and sun protection behaviors will be mediated by melanoma knowledge, self-efficacy for SSE and sun protection behaviors, perceived benefits of SSE and sun protection behaviors, perceived benefits of SSE and sun protection behaviors, perceived benefits of SSE and sun protection behaviors, and perceived controllability of melanoma. For each potential mediator, the four component steps (Frazier et al., 2004; Mallinckrodt et al. 2006) will be examined via logit models (for the SSE outcome) and linear models (for the sun protection behaviors outcome). Using Krull and colleagues' approach for multilevel models (Krull & Mackinnon, 2001), we will calculate the product of the two pieces of the mediating path (from intervention group assignment to mediating variable and from mediating variable to outcome), with the outcomes at 24 weeks as the primary focus (and 48 weeks outcomes examined secondarily). Bootstrap procedures will be utilized to formally test for significance of the mediating pathway (Mallinckrodt et al. 2006; Shrout & Bulger, 2002). Imputation will be used to evaluate the robustness of the results to missing data, assuming dropouts are MAR as well as MNAR.

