5.3. Exploratory Aim

Aim 3. To examine moderators of the impact of the intervention. Research Question. To evaluate whether ITW effects are moderated by the following factors: time since diagnosis; disease stage; age; sex; income; education; Internet experience; distress about melanoma; worry about recurrence; and evaluation and usage of the ITW. To examine this aim, we will incorporate interactions between the effect of intervention and potential moderators into the multilevel models described for Aim 1, with the outcomes at 24 weeks as the primary focus (and 8 week and 48 week outcomes examined secondarily). In order to minimize the significance due to multiple testing, variables with low variability in the sample will be eliminated from consideration, and Hochberg's step-down procedure for multiple testing will be employed for the remaining candidates for moderators. Again, imputation will be used to evaluate robustness of the results to missing data, assuming dropouts are MAR as well as MNAR.

Additional Analyses. Using the same analytic approach as for Aim 1, we will examine the impact of the intervention on the number of health care visits. We will use multilevel models similar to those described in Aim 1 to compare changes from baseline to follow-up in distress about melanoma, worry about melanoma recurrence, and perceived risk of melanoma recurrence for the ITW and Usual Care groups. Descriptive statistics, including means and standard deviations or relative frequencies will be used to summarize the indicators of study feasibility (ineligibility rate/reasons, recruitment rate/reasons for refusal, differences in sociodemographic and medical factors between study decliners and those recruited, dropout rate and reasons, and use of the intervention website). Additionally, we will use chi-square and regression analyses to examine retention rates and usage of the ITW vary according to patient income and education.

6. Data and Safety Monitoring

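### The MNAR grid for the sun protection index contradicts its own description: as written, ITW dropouts keep 25% to 100% of the effect, and the no-effect case is never run

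*Combined protocol and SAP*

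**What the plan says.** Section 5.1 (Primary Aim) uses weighted generalized estimating equations (GEE) as the main analysis, assuming dropout is missing at random. Multiple imputation under MNAR scenarios follows as a secondary analysis. For the sun protection behavior index the imputation rule is explicit: "the mean for treated dropouts will be assumed equal to the estimated mean for Usual Care non-dropouts plus a sensitivity parameter". The parameter is "set at values of 25%, 50%, 75% and 100% of the estimated treatment effect (representing scenarios ranging from dropouts experiencing almost all to none". The sentence thus glosses its four values as running from dropouts who get nearly the whole effect to dropouts who get none of it.

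The planning values are in section 3.6 (Sample Size). In the prior trial, scores "increased to 3.2 and 3.4 for the generic and tailored interventions, respectively". For the present Usual Care arm, "we assume that the sun protection scores in that group would increase to a maximum of 3.0". On attrition: "We anticipate that at least 378 of the 420 patients (i.e., 90%) will complete the 24 weeks post-baseline assessment".

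Sections 5.2 and 5.3 also call for MNAR imputation for the mediator and moderator analyses, but give no values. The grid in section 5.1 is therefore the only one in the documents. Whether it is to be reused for those aims is not stated.

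**The concern.** The formula and its gloss disagree. A parameter added to the Usual Care mean measures how much of the effect a dropout retains, so 25% to 100% means a quarter to all of it. Neither end fits the description: 100% is the whole effect rather than nearly all of it, and 25% is not zero. Reading the list backwards does not help, because the lowest value is still 25%.

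These runs exist to show how far informative dropout could bias the result. If the formula is programmed literally, the harshest case the plan says it covers is absent, and one of the four runs (100% kept) applies essentially no penalty. The text does not label individual runs. If the percentages and the gloss are read in the same order, which is an inference, the most lenient run would be the one reported as the no-effect scenario. A reader could then be told that the result survived a worst case that was never run.

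**Working it through.** **Inputs**
- Anchor and grid: section 5.1, parameter k = 0.25, 0.50, 0.75, 1.00 of the estimated effect D.
- Planning scores: section 3.6, 3.4 (tailored arm of the prior trial, taken here as the ITW value) and 3.0 (Usual Care), so D = 3.4 − 3.0 = 0.4.
- Dropout: section 3.6, 10% at 24 weeks overall, applied here to the ITW arm. 420 × 0.90 = 378 completers, or 189 per arm.
- SDs of 0.66 at baseline and 0.76 at follow-up, correlation 0.60: section 3.6.

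**Step 1. Does the rule give the described range?**
Share kept = (dropout mean − Usual Care mean) / D = k. The rule therefore gives 25%, 50%, 75% and 100% kept, for any value of D. The described range, ending at 0%, is not reproduced. It is reproduced exactly if the listed percentages are the share lost: 1 − k = 75%, 50%, 25%, 0% kept.

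**Step 2. Dropout means on the planning scores**
- As written: 3.0 + (0.25, 0.50, 0.75, 1.00) × 0.4 = 3.1, 3.2, 3.3, 3.4.
- As described: 3.4 − (0.25, 0.50, 0.75, 1.00) × 0.4 = 3.3, 3.2, 3.1, 3.0.

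Three of the four scenarios coincide. The difference is that 3.4 (all kept) is run in place of 3.0 (none kept).

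**Step 3. Effect on the overall estimate**
Suppose Usual Care dropouts resemble Usual Care completers and D equals the non-dropout difference. With ITW dropout d, the overall effect as a share of D is (1 − d) + d × k.

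| ITW dropout d | Harshest run as written (k = 0.25) | Described worst case (k = 0) |
|---|---|---|
| 10% (planned, 24 weeks) | 0.925 | 0.900 |
| 15% (48-week attrition) | 0.8875 | 0.850 |
| 20% (assumed) | 0.85 | 0.80 |
| 30% (assumed) | 0.775 | 0.70 |

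At 10% and D = 0.4 this is 0.37 against 0.36. The plan does not say that the grid will be applied at 48 weeks, so the 15% row is conditional on that.

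**Step 4. Could a conclusion change?**
- SD of change = √(0.66² + 0.76² − 2 × 0.60 × 0.66 × 0.76) = 0.641.
- SE = 0.641 × √(2/189) = 0.066.
- z = 6.06 with no penalty, 5.61 at k = 0.25, 5.46 at k = 0.

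At the planned effect, nothing changes. With the SE held fixed and a two-sided 0.05 level (assumed; the documents state no alpha), the two harshest cases disagree only if the unpenalised z lies between 1.96/0.925 = 2.12 and 1.96/0.900 = 2.18.

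**The case against.** The strongest reply is that this is a wording slip with almost no numerical consequence. It sits in a secondary sensitivity analysis of one of two primary outcomes, three of the four runs are the same either way, and the window in which a conclusion could differ is 0.06 wide in z. All of that stands, and it limits the weight of the point. It does not remove the contradiction.

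A second reply is that the parenthesis states the intent, so the programmer may well treat the percentages as the share lost and run the no-effect case after all. That is plausible, and the exact match in Step 1 suggests that the slip lies in the formula rather than in the percentages. But the documents do not show which version would be programmed, and the explicit instruction is the formula. The statement that the case is never run holds only for the rule as written.

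Third, the z values hold the SE at its completer value, whereas multiple imputation would give a different SE; and the 20% and 30% dropout rates are illustrative. Both points are fair. The shares of effect kept do not depend on the SE, and only the 10% row rests on the plan's figure for the primary time point.

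Finally, a run with 100% kept is not wrong in itself. It is a near-reference case. The substantive gap is the absent 0% case.

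**Conclusion.** The concern holds. The stated rule cannot produce the range that the same sentence claims, and nothing elsewhere in the documents corrects it. As written, the plan omits its own worst case and runs an essentially unpenalised case in its place.

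The size is small: 0.025 of the effect at 10% ITW dropout (0.01 points on a planned difference of 0.4), rising to 0.05 at 20% and 0.075 at 30%. These figures assume that ITW dropout matches the overall rate at the planned 10%, that Usual Care dropouts resemble Usual Care completers, and that the estimated effect equals the non-dropout difference. The contradiction itself needs none of these assumptions. The correction should be made, but the primary test and sample size do not depend on it.

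**What to change.** The sponsor should state which meaning was intended and correct the sentence in section 5.1. Either of two wordings gives the described scenarios with four runs:

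1. Keep the Usual Care non-dropout mean as the anchor and set the parameter at 75%, 50%, 25% and 0% of the estimated effect.
2. Subtract 25%, 50%, 75% and 100% of the estimated effect from the ITW non-dropout mean.

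The two are identical when the estimated effect equals the non-dropout difference. The weighted GEE estimate may differ from that difference, and then only the first guarantees that the no-effect case places ITW dropouts exactly at the Usual Care non-dropout mean. It also keeps the plan's stated anchor, so it is the simpler choice. Adding 0% to the existing list would supply the missing case too, at the price of one more run and an amended description.

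The cost of either numbered option is one corrected sentence and no extra runs. The harshest sensitivity result may look slightly less favourable.
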